#### 16.2.2. SENSITIVITY ANALYSES FOR KEY SECONDARY EFFICACY ENDPOINTS

The analysis of the Key Secondary Efficacy Endpoint of proportion of Subjects with Respiratory Failure or Death (RFD) by Day 28 will be repeated with missing values treated as follows:

- If there is no ordinal scale value because the subject discontinued prior to Day 28, then the subject will be assumed as RFD.
- If a subject has been discharged prior to Day 28 then they would be assumed as NO RFD.

Document: \\[REDACTED]\net\enterprise\Apps\sasdata\SASb\SAS\Atea\_Pharmaceuticals\AT-527\ISZA63631\Biostatistics\Documentation\SAP\AT-03A-001\_V1.0\_COVID\_SAP\_PA7.doc  
Author: [REDACTED] Version Number: V1.0  
Template No.: CS\_TP\_BS016 Revision 6 Version Date: 15Apr2021  
Effective Date: 02Dec2019 Reference: CS\_WI\_BS005

Copyright © 2009, 2010, 2012, 2016, 2018, 2019 [REDACTED] All rights reserved. The contents of this document are confidential and proprietary to [REDACTED] Holdings Inc. and its subsidiaries. Unauthorized use, disclosure or reproduction is strictly prohibited.

- If a subject is still on study and in the hospital at Day 28 but with no scale score at Day 28 they will be excluded from the denominator.

### 16.2.3. OTHER SECONDARY EFFICACY ENDPOINTS

#### 16.2.3.1. Proportion of Subjects Improving/Worsening from Baseline in Clinical Status Using the NIAID Ordinal Scale by Day 5 and 14

The endpoint is based on the lowest observed value on the clinical status (NIAID) scale between D1 to D5 and D1 to D14. Subjects will be classified as “improved”, “same” or “worsened compared to Baseline.

#### 16.2.3.2. All-cause Mortality

A secondary endpoint is the all-cause mortality i.e., the proportion of subjects who died during the study including the follow-up visits regardless of the cause of death. Death may occur after the 14-day primary study period as some subjects might remain on prolonged ventilation before recovering or dying. Mortality will be assessed at Day 10, 14, 28 and 63. Subjects who are discontinued from the study for a reason other than death, prior to each of Day 10, 14, 28 and 63 will be excluded from the denominator.

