8.1.2. Intention To Treat Population

The intention to treat (ITT) population will include all randomized subjects and will be analyzed as randomized.

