### 16.1.3. PRIMARY ANALYSIS OF PRIMARY EFFICACY ENDPOINT

The primary efficacy goal is to reduce the incidence of PRI by 50% for active-dosed subjects compared to placebo recipients. Number and proportion of subjects with and without PRI during the 14-day primary study period will be provided by treatment group based on the ITT analysis set. The difference between the treatment groups will be presented with corresponding 95% CI. A Cochran-Mantel-Haenszel (CMH) general association test will be used to test for differences in rates between the treatment groups controlling for geographic region (see [Section 7.6](#)).

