(Note: Examples include recovered subjects needing inpatient quarantining/confinement or needing social services connections for outpatient living).
7. Not hospitalized, but with limitation on activities and needing close outpatient care for COVID-19 manifestations.
8. Not hospitalized, no limitations on activities, no need for continued close medical care.

#### 16.2.1.3. Proportion of Subjects with Respiratory Failure or Death (RFD) by Day 28

The third key secondary endpoint is proportion of subjects with RFD on or before Day 28, which is defined as progression to respiratory support level 5 (requiring intubated mechanical ventilation or ECMO) or 6 (death) (Section 16.1.1). The data will be reported on the Ordinal Scale of Respiratory Support Level and Death Details pages of the eCRF. Proportion of subjects with RFD on or before Days 10, 14, and 63 will also be analyzed. Missing values will be treated as follows:

- If there is no ordinal scale value because the subject discontinued prior to Day 28, then the subject will be assumed as NO RFD.
- If a subject has been discharged prior to Day 28 then they would be assumed as NO RFD.
- If a subject is still on study and in the hospital at Day 28 but with no scale score at Day 28 they will be excluded from the denominator.

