#### 16.2.5. ANALYSIS OF OTHER SECONDARY EFFICACY ENDPOINTS

The distribution of subjects improved/the same/worsened from baseline in clinical status will be compared between treatment groups at Day 5 and Day 14 with a Mann-Whitney nonparametric test. The lowest observed value on the clinical status (NIAID) scale during between D1 to D5 and D1 to D14 will be used.

The number and percentage of subjects who have "improved", "same" or "worsened" based on their lowest NIAID ordinal scale between D1 to D5 and D1 to D14 will also be presented.

Document:	\[REDACTED]\net\enterprise\Apps\sasdata\SASb\SAS\Atea_Pharmaceuticals\AT-527\SZ\A63631\Biostatistics\Documentation\SAP\AT-03A-001_V1.0_COVID_SAP_PA7.doc		
Author:	\[REDACTED]	Version Number:	V1.0
		Version Date:	15Apr2021
Template No.:	CS_TP_BS016 Revision 6	Reference:	CS_WI_BS005

Effective Date: 02Dec2019

Copyright © 2009, 2010, 2012, 2016, 2018, 2019 \[REDACTED] All rights reserved. The contents of this document are confidential and proprietary to \[REDACTED] Holdings Inc. and its subsidiaries. Unauthorized use, disclosure or reproduction is strictly prohibited.

The proportion of subjects who died during the study regardless of the cause of death will be analyzed in the same manner as the primary efficacy endpoint at Day 10, 14, 28 and 63.

Kaplan-Meier curves (product-limit estimate) will be provided by treatment arm for the duration of hospitalization for COVID-19 (days), for the time to sustained non-detectable SARS-CoV-2 (days) and the time to first SARS-CoV-2 negative test (Days). Kaplan-Meier estimate of the time will be provided at the 25th, 50th (median), and 75th percentiles along with their corresponding two-sided 95% CIs. The estimates of the SEs will be computed using the Greenwood's formula, the CI for the median will be calculated according to Brookmeyer and Crowley (1982), and the CIs for the survival function estimates at each scheduled time point will be derived from the Kaplan-Meier estimates using the log-log transformation.

The p-value associated with the log-rank test statistic will be provided and compared at the two-sided 0.05 alpha level based on a null hypothesis that there is no difference between the two treatment groups and will be presented for descriptive purpose only. For the time to sustained non-detectable SARS-CoV-2 (days) and the time to first SARS-CoV-2 negative test (Days), separate analyses will be performed for:

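### SAP V1.0 removes subjects who left the study alive from each mortality denominator but keeps every death, which can overstate mortality in the arm with more leavers

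*SAP*

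**What the plan says.** SAP 16.2.3.2 defines all-cause mortality as the proportion who died from any cause, follow-up visits included, and states: "Mortality will be assessed at Day 10, 14, 28 and 63". It then sets the denominator rule. The subjects concerned are "Subjects who are discontinued from the study for a reason other than death, prior to each of Day 10, 14, 28 and 63"; they "will be excluded from the denominator".

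SAP 16.2.5 says that the proportion who died "will be analyzed in the same manner as the primary efficacy endpoint at Day 10, 14, 28 and 63". The primary analysis (SAP 16.1.3) compares proportions with a difference, a 95% CI and a CMH test by region, and its results "will be provided by treatment group based on the ITT analysis set". Protocol 8.1.2 says the ITT population "will include all randomized subjects and will be analyzed as randomized".

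Two neighbouring endpoints treat leavers differently:
- **Primary endpoint (SAP 16.1.2).** Early discontinuers stay in and are assigned an outcome according to their reason for leaving. Recovery is one of the listed reasons.
- **RFD (SAP 16.2.1.3).** "If there is no ordinal scale value because the subject discontinued prior to Day 28, then the subject will be assumed as NO RFD". The sensitivity analysis in 16.2.2 reverses this assumption: "then the subject will be assumed as RFD".

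No sensitivity analysis is given for mortality. SAP 16.2.6 repeats the mortality analysis by cause of death, so the rule carries over there.

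**The concern.** A subject who leaves alive is known to have survived to the last contact. The rule discards that follow-up at every later time point, while each death keeps its place in numerator and denominator. The set compared is then no longer the randomized one, and it changes between Days 10, 14, 28 and 63.

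The removal can depend on outcome. A subject who recovers and leaves counts as a good result for the primary endpoint and for RFD, yet disappears from the mortality comparison. If one arm has more such subjects, its denominator shrinks and its mortality proportion rises with no additional death. Mortality is a prespecified secondary endpoint and clinically the weightiest outcome in the plan, so a distortion against the arm with more recoveries deserves correction even if it is small.

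**Working it through.** **Inputs from the documents.** Neither document states a mortality rate, a per-arm withdrawal rate or a power for this endpoint. The planned size is 91 per arm (SAP 7.1), and Part A stopped at 81 randomized, about 40 per arm. The Protocol synopsis raises 182 to 190 for dropouts and baseline-negative subjects together: (190 − 182)/190 = 4.2%.

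**Reproducing the 91 per arm.** For rates 0.4 and 0.2, one-sided 0.025, power 0.8:
- Uncorrected: [1.96·√(2·0.3·0.7) + 0.842·√(0.24 + 0.16)]² / 0.2² = 81.2, so 82.
- Continuity-corrected: (81.2/4)·[1 + √(1 + 4/(81.2·0.2))]² = 90.9, so 91 per arm and 182 in total.
- Exact Fisher power at 91 per arm is 80.8%, so the planned size checks.

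**Effect of the rule with equal deaths.** All mortality and withdrawal figures from here on are assumptions. Reported mortality in an arm is deaths/(n − left alive). With 91 per arm and 5% versus 20% leaving alive (5 versus 18 subjects), the denominators are 86 and 73.

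| Deaths per arm | Fewer leavers | More leavers | Gap (points) | All randomized | Nominal p |
|---|---|---|---|---|---|
| 2 | 2/86 = 2.33% | 2/73 = 2.74% | 0.41 | 2.20% | 0.87 |
| 4 | 4/86 = 4.65% | 4/73 = 5.48% | 0.83 | 4.40% | 0.81 |
| 9 | 9/86 = 10.47% | 9/73 = 12.33% | 1.86 | 9.89% | 0.71 |

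The ratio is 86/73 = 1.18 throughout. At 0% versus 5% leaving, nearer the 4.2% allowance, it is 91/86 = 1.06, with gaps of 0.13 to 0.58 points for 2 to 9 deaths.

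At 40 per arm, with 4 deaths each before Day 14 and 2 versus 8 leaving alive at Day 14, the rule gives Day 28 mortality of 4/38 = 10.5% versus 4/32 = 12.5%. Kaplan-Meier gives 1 − 36/40 = 10.0% in both arms.

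**When the bias appears.** Let p be true mortality in both arms, f the share of deaths that precede withdrawal, and w the withdrawal proportion among those then alive, unrelated to risk. The rule estimates

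[pf + p(1 − f)(1 − w)] / [1 − w(1 − pf)].

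For p = 5%, w = 5% versus 20%:
- f = 1: 0.05/0.9525 = 5.25% versus 0.05/0.81 = 6.17%, gap 0.92.
- f = 0.5: 0.04875/0.95125 = 5.12% versus 0.045/0.805 = 5.59%, gap 0.47.
- f = 0: the expression reduces to p, gap 0.

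At f = 1 the gap is 0.38 for p = 2% and 1.72 for p = 10%.

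**Type I error.** In 100,000 simulated trials (91 per arm, unstratified two-sided 0.05 test, all deaths before withdrawal), 5% versus 20% withdrawal gave 3.2%, 5.7% and 6.5% for mortality of 2%, 5% and 10%. Withdrawal of 5% in both arms gave 3.7%, 4.8% and 5.1%. An extreme 5% versus 40% gave 6.6%, 11.2% and 15.8%.

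**The case against.** Several points count against a strong reading, and most of them stand.

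- **Delivered results.** A reader might infer that reported mortality is distorted. The documents do not support that. The changes form of 16 March 2022 lists all-cause mortality among the SAP analyses not presented, and says Part B patients are only listed. The same form says the SAP will not be updated, so the rule remains in V1.0.
- **Who is removed.** A reader might infer that anyone who leaves alive drops out of the endpoint altogether. The rule works per time point: a subject leaving on Day 20 still counts at Days 10 and 14. It also concerns leaving the study, whereas Protocol 5.7 encourages subjects who only stop treatment to stay in follow-up.
- **Whether imbalance is enough.** A reader might infer that unequal withdrawal by itself produces a mortality difference. The f = 0 case shows otherwise: timing or a link to risk is also needed.
- **Size and stakes.** The gaps are small, and Protocol 1.1 reports low progression rates. SAP 7.4 gives other secondary endpoints only nominal p-values, and SAP 4.2 accepts that efficacy results may be regarded as exploratory after the interim look.
- **Other views of death.** V1.0 also had RFD with its sensitivity analysis, and a death summary on the safety set in SAP 17.2 with no such exclusion. The form lists both among the outputs not presented.
- **The remedy is imperfect.** Kaplan-Meier assumes non-informative censoring, which leaving because of recovery can violate. Extend the 40-per-arm example with 2 later deaths per arm among those remaining, all leavers surviving. True mortality is 6/40 = 15.0% in both arms. Kaplan-Meier gives 1 − 0.9·(32/34) = 15.3% versus 1 − 0.9·(26/28) = 16.4%. The rule gives 6/38 = 15.8% versus 6/32 = 18.8%. The bias shrinks but does not vanish.

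These points limit the scope and size of the concern. They do not justify a rule that removes only survivors from an analysis modelled on the ITT set.

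**Conclusion.** The concern holds as a flaw in SAP V1.0. The mortality denominator departs from the ITT set that 16.2.5 and 16.1.3 imply, is inconsistent with the RFD rule, lacks a sensitivity analysis, and can push mortality upward in the arm with more early leavers.

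The distortion is modest under plausible assumptions: a ratio of about 1.06 to 1.18, and under 2 points at 91 per arm for up to 9 deaths per arm. Type I error moves little unless withdrawal is very unequal. These sizes rest on assumed mortality and withdrawal rates and, for the largest gaps, on all deaths preceding withdrawal. The point matters for the wording of V1.0 and for any mortality figure later reported under it.

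**What to change.** Replace the denominator rule in SAP 16.2.3.2, and the matching sentence in 16.2.5, as follows:

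1. Keep all ITT subjects. Estimate mortality at Days 10, 14, 28 and 63 by Kaplan-Meier, censoring at the date last known alive, and report the between-arm difference with its 95% CI. Apply the same denominator principle to the cause-of-death analyses in 16.2.6.
2. Add a sensitivity analysis with all randomized subjects in the denominator: leavers counted as alive, plus best-case and worst-case bounds. With 91 per arm, 4 deaths each and 5 versus 18 leavers, the bounds are 4/91 to 9/91 (4.40% to 9.89%) versus 4/91 to 22/91 (4.40% to 24.18%). Counting leavers as alive is not neutral if later deaths go unseen: for p = 5% and f = 0.5, p[f + (1 − f)(1 − w)] gives 4.88% at w = 5% and 4.50% at w = 20%.
3. Report deaths learned of after withdrawal in that sensitivity analysis, unless vital status is sought equally in both arms. The documents describe no vital-status follow-up after study withdrawal.

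The cost is SAP wording and a little extra programming. Date of death is recorded (Protocol 6.9), an end-of-study date already serves for censoring in SAP 16.2.3.3, and Kaplan-Meier methods are already specified in 16.2.5. The price is the censoring assumption, which step 2 is there to test. Since the analysis was dropped, a note that the V1.0 rule should not be used if mortality is reported would be enough.

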#### 16.2.3.3. Duration of Hospitalization for COVID-19 (days)

A secondary endpoint is the duration of hospitalization/confinement in days, defined as the time from start of treatment to either achieving Status 7 or 8 on the NIAID Clinical Status scale or hospital discharge (which ever happens first). Data from the follow-up period after Day 14 will be included. This endpoint will be calculated as follows:

- Duration of Hospitalization for COVID-19 (days) = ((Date of achieving status 7 or 8 OR hospital discharge) – Study Day 1) +1

Subjects who don't achieve status 7 or 8 nor have hospital discharge will be censored at end of study (EOS).

Subjects who die will be censored to the latest EOS date available.

#### 16.2.3.4. Time to Sustained Non-detectable SARS-CoV-2 (days)

A secondary endpoint is the time to sustained nondetectable SARS-CoV-2 RNA from randomization in days,

Document: \\[REDACTED]\net\enterprise\Apps\sasdata\SASb\SAS\Atea\_Pharmaceuticals\AT-527\SAZ\A63631\Biostatistics\Documentation\SAP\AT-03A-001\_V1.0\_COVID\_SAP\_PA7.doc

[figure not shown]
Author: [REDACTED] Version Number: V1.0  
Version Date: 15Apr2021

Template No.: CS\_TP\_BS016 Revision 6

Reference: CS\_WI\_BS005

Effective Date: 02Dec2019

Copyright © 2009, 2010, 2012, 2016, 2018, 2019 [REDACTED] All rights reserved. The contents of this document are confidential and proprietary to [REDACTED] Holdings Inc. and its subsidiaries. Unauthorized use, disclosure or reproduction is strictly prohibited.

calculated as follows:

- Time to sustained nondetectable SARS-CoV-2 (days) = (Start date of sustained nondetectable SARS-CoV-2 – Date of randomization) +1

The SARS-CoV-2 test results during the study will be captured by the Central Laboratory. The start date of sustained nondetectable SARS-CoV-2 is defined as the earliest date when the test result is negative and remains negative until end of the study or D14 as the test is not required after that day.

Analysis of this endpoint will be performed on the mITT analysis set only. Both COBAS and TaqPath assays report results as detectable or non-detectable. Each method has its own limit of detection. The analyses will be performed separately on results from each assay.

The following algorithm will be followed to determine how a subject which didn't meet the event (i.e., Non-detectable SARS-CoV-2) should be censored:

1. If the subject has no post-baseline SARS-CoV-2 test results, the subject will be censored at the date of first dose of study drug;
2. If the subject's SARS-CoV-2 test remain positive during the study, the subject will be censored at the date of their latest of SARS-CoV-2 test with a non-missing result;
3. If the subject has negative SARS-CoV-2 but not sustained, i.e. the negative result was not confirmed at a later scheduled visit (due to missing data, early discontinuation, study completion, etc.), the subject will be censored at the date of their latest SARS-CoV-2 test date with a non-missing result;
4. If subject has missing baseline SARS-CoV-2 data, but has a post-baseline positive SAS-CoV-2 test result, the subject will be considered SARS-CoV-2 positive at baseline. Otherwise, a subject with missing baseline data will be censored at Day 1.
5. If subject has negative SARS-CoV-2 at baseline, the subject will be censored at Day 1.

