a) Prior to the first dose b) Height at Screening only. c) For females of childbearing potential: serum pregnancy test at Screening. d) Collected at same time as safety lab draw. e) ET=Early Termination f) As quarantine and other factors may limit the subject's ability to return to the clinic, the follow-up assessments may be conducted by telephone, video platform or at-home visits by trained medical professional(s) (with a ± 2 day window). If this follow-up is done by telemedicine, no SARS-CoV-2 samples will be collected. g) Optional h) See [Section 6.9](#) for details of assessments, including ordinal scales for overall Clinical Status and Respiratory Support. i) Not necessary if subject already discharged from hospital j) After discharge, cardiac ECG parameters will be collected on outpatients. k) After discharge, pulse oximetry to be done on Days 2-6,8,10,12, and 14, or more frequently as needed if SpO2 < 93% l) Chest imaging (chest x-ray, CT scan, etc.) will be obtained ideally at Screening but can occur within 48 hours before screening as long as the clinical status of the subject has not changed, in the opinion of the investigator. m) Dosing on Day 1 can occur at any time of day (AM or PM). n) Collect prior to the 3rd dose (on Day 2). o) Collect prior to the 5th dose (on Day 3).

Protocol Number: AT-03A-001

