6.6. COVID-Specific Tests

Diagnostics and SOC treatment of COVID-19 are constantly evolving. The current protocol targets capture of COVID-specific parameters known to be important or potentially important at this time:

- SARS-CoV-2 qualitative testing. At Screen, subjects will typically have been identified as presumptively SARS-CoV-2 infected. The initial local SARS-CoV-2 test result will be confirmed at Screening by one of the FDA-EUA assays. The FDA-EUA assay will be used to assess SARS-CoV-2 viral presence in nasopharyngeal (preferentially) or throat swabs at periodic timepoints in this study, as indicated in [Table 6-1](#). As this may be a relatively uncomfortable procedure for some subjects, and such sampling is biohazardous for caregivers, it is acknowledged that some subjects may not be able to provide samples for all timepoints listed. Although sampling should be encouraged at all timepoints listed through Day 14, key SARS-CoV-2 testing assessments are at Screening, Day 5 and Day 14. Sampling during follow-up is supplemental, to be collected as feasible, considering those visits are likely to be conducted via telemedicine.
- Residual eluates (in solution) from nasopharyngeal or throat swabs obtained for SARS-CoV-2 may be stored frozen for eventual quantitative testing, possible resistance analyses, and viral infectivity assays if the additional handling and storage do not impose undue exposure biohazards for site staff and the central laboratory.
- Serologic D-dimer levels, a reflector of a potential hyper-coagulopathy that is common in COVID-19 patients, for future exploratory analyses. Note: If the site uses D-dimer levels for patient management, separate D-dimer levels can be obtained locally as available, at investigator preference per their local standard of care.
- Stored serum or plasma samples will be collected for possible eventual analyses of various cytokines (including interleukin-6), antibody to SARS-CoV-2, other relevant COVID-specific tests (e.g. C-reactive protein) or SARS-CoV-2 tests (e.g. antibody tests), as reliable validated assays become available.

Protocol Number: AT-03A-001

Note: In an effort to standardize the method for collection of nasopharyngeal samples during the study, the same nostril in an individual subject should be used (if possible) if only one nostril will be sampled.

The sampling schedule for the above tests is specified in [Table 6-1](#).

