**Table B: Analysis Visit Windows**

Scheduled Visit	Target Day of the Visit	Analysis Visit Window
Analysis visit windows for safety labs and SARS-CoV-2 Test		
Baseline	Day 1	Day -1 or Day 1/before 1 st dose
Day 2	Day 2	Day 2 to Day 3
Day 5	Day 5	Day 4 to Day 6
Day 8	Day 8	Day 7 to Day 9
Day 10	Day 10	Day 10 to Day 11
Day 12	Day 12	Day 12 to Day 13
Day 14	Day 14	Day 14 to Day 18
Day 21	Day 21	Day 19 to Day 25
Day 28	Day 28	Day 26 to Day 46
Day 63	Day 63	Day 47 to Day 79

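### SAP 16.2.3.4: for a first negative swab at Day 14, censoring rule 3 conflicts with the endpoint's own definition

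*SAP*

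**What the plan says.** SAP 16.2.3.4 sets out this endpoint in three steps.

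- **Definition.** The start date is the earliest test that "is negative and remains negative until end of the study or D14 as the test is not required after that day". Time runs from randomization to that date, plus one day.
- **Lead-in to the censoring algorithm.** The five rules that follow determine "how a subject which didn't meet the event (i.e., Non-detectable SARS-CoV-2) should be censored".
- **Rule 3.** It covers a subject with a negative that was not sustained, and explains this as meaning that "the negative result was not confirmed at a later scheduled visit (due to missing data, early discontinuation, study completion, etc".) For such a subject, "the subject will be censored at the date of their latest SARS-CoV-2 test date with a non-missing result".

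On sampling, Protocol 6.6 says that "key SARS-CoV-2 testing assessments are at Screening, Day 5 and Day 14", and adds: "Sampling during follow-up is supplemental, to be collected as feasible, considering those visits are likely to be conducted via telemedicine". Footnote f of Protocol Table 6-1 says of the follow-up visits: "If this follow-up is done by telemedicine, no SARS-CoV-2 samples will be collected". Protocol 8.2.3 names the endpoint but does not define sustained.

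SAP 16.2.5 plans Kaplan-Meier curves and a log-rank p-value for descriptive purposes. The Changes to Planned Statistical Analyses Form (16 March 2022) keeps the endpoint as Table 14.2.5.4, shown separately for COBAS and TaqPath. It also says that the interim outputs serve as the final delivery, that Part B is listed only, and that the SAP stays as it is.

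**The concern.** Section 16.2.3.4 gives sustained two meanings. Under the definition, a negative that holds to Day 14 is enough, because no test is required after that. Under rule 3, a negative needs confirmation at a subsequent planned visit, and study completion does not excuse its absence. The meanings part for a subject whose first negative is the Day 14 swab and who has no later swab: an event under one, censored under the other.

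Read literally, rule 3 would also make event status at Day 14 depend on whether a supplemental follow-up swab happened to be taken. That reflects visit logistics, not viral clearance. At stake are the event counts and the last required step of the curve in a table that is still to be delivered.

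**Working it through.** The SAP gives no event count, power or sample size for this endpoint, so there is no figure to reproduce. The check applies both texts to each swab pattern that could matter.

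| Pattern | Definition | Rule 3 read literally | Agree? |
|---|---|---|---|
| Negative on Day 12 and Day 14, no later swab | Event at Day 12 | Confirmed at Day 14, so event at Day 12 | Yes |
| Negative on Day 12, no swab afterwards | Not shown to hold to Day 14 | Censored at Day 12 | Yes |
| First negative on Day 14, later swab also negative | Event at Day 14 | Confirmed, so event at Day 14 | Yes |
| First negative on Day 14, no later swab | Event at Day 14 | Unconfirmed, so censored at Day 14 | **No** |

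Only the last row conflicts.

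**Effect on the time.** Let R be the randomization date and S the date of the Day 14 swab.

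- Definition: event at (S − R) + 1.
- Rule 3: censored at the latest non-missing test. With no later swab this is also S, giving (S − R) + 1.
- Difference: 0 days. The event flag is 1 under the definition and 0 under rule 3.

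Under SAP 6.1, Study Day 14 falls 13 days after the first dose. A subject dosed on the day of randomization has 13 + 1 = 14 days under both readings. A subject dosed the day after has 14 + 1 = 15 days under both.

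**Effect on the curve.** Because the times are identical, so are the numbers at risk at every time. At the Day 14 swab, let n be the number at risk, a the first negatives with a later confirming swab, and b those without one. The Kaplan-Meier factor is

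- 1 − (a + b)/n under the definition;
- 1 − a/n under rule 3.

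Earlier steps do not move, and only the Day 14 contribution to the log-rank statistic changes. The documents give none of n, a or b for this table, so the difference b/n cannot be evaluated.

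**Does study completion point to Day 14?** Protocol Section 6 counts the follow-up visits from study completion at Day 14, and Protocol 8.3.1 also equates study completion with Day 14. Protocol 5.7, by contrast, ends an individual's study at the 49-day follow-up visit. A programmer could therefore reasonably take rule 3 to cover the Day 14 case.

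**The case against.** The strongest reply is that the SAP already supplies an order. The event is defined first, and the lead-in sends only subjects without the event to the censoring rules. The definition deals with Day 14 expressly, so a subject negative on that swab never reaches rule 3. This largely stands, and it makes the definition the better reading. A reader might infer that the SAP is silent on which text comes first; the lead-in shows that this is too strong. It does not remove the inconsistency, however. The lead-in glosses the event as non-detectable, without sustained. On that gloss nobody with a negative would reach rule 3, although rule 3 is written for such subjects. Rule 3 also supplies its own meaning of not sustained, which the definition contradicts.

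Second, rule 3 has proper work before Day 14. A subject may be negative at Day 8, 10 or 12, be followed by telephone after discharge (Protocol Section 6), and complete without a Day 14 swab. Study completion fits that case too. This stands, and it is why rule 3 should be narrowed, not deleted.

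Third, SAP Table B lists Days 21, 28 and 63 under "Analysis visit windows for safety labs and SARS-CoV-2 Test". A reader might infer that these are confirmation visits for this endpoint. Table B is a windowing table for mapping results to visits, and it does not say so. It shows only that later visits exist to which rule 3's wording could attach.

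Fourth, the output shells and table footnotes are not among the documents, so they may already state the rule. That is fair. The claim is only that the protocol, SAP and changes form do not record it.

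**Conclusion.** The definition and rule 3 are inconsistent for one pattern: a first negative on the Day 14 swab with no later swab. The lead-in favours the definition. The event flag and the Day 14 Kaplan-Meier step depend on the reading; the time does not.

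Severity is minor. The endpoint is other-secondary, its p-value is descriptive and outside the gatekeeping in SAP 7.4, and only the Part A table is concerned. No size of effect is claimed, because no document shows that any subject was censored this way.

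A reader might infer a large effect from the interim results in Protocol 1.1. In the subset with baseline viral load at or above the median, placebo clearance was 0% at Days 2, 8, 10 and 12 and about 22% at Day 14; for AT-527 it was 31% at Day 12 and about 47% at Day 14. It is tempting to conclude that rule 3 would erase every placebo event, or carry the log-rank p-value across 0.05. The documents do not support either. These are visit proportions without denominators, the assay is not stated, no Day 5 figure is given, the number of later swabs is unknown, and the form does not say that an above-median version of the table is delivered.

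**What to change.** 1. State in the changes form that the definition in SAP 16.2.3.4 governs.
2. Reword the confirmation clause of rule 3 to cover only a negative before Day 14 with no later swab through Day 14, and not a negative on the Day 14 swab. A negative that reverts to positive by Day 14 fails the definition anyway and should stay censored.
3. Record in the changes form, and in the footnote of Table 14.2.5.4 for both COBAS and TaqPath, which rule the reused interim programs applied.
4. Apply the same rule to the infectious-titer table (14.2.5.6), which the form says follows the approach of the sustained non-detectability output.

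The cost is a short entry in the form and a footnote per table. A rerun is needed only if the programs censored Day 14 negatives. The downside is that single unconfirmed negatives at Day 14 count as events. Both timing options shown on the form fall after unblinding, so the entry should be presented as applying the existing definition, not as a new choice.
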